#### 7.4.1. End-of-Treatment Disease Evaluation(s)

Disease evaluation is to be performed as outlined in Section 7.3.8 within 30 ( $\pm$  3) days of last dose of study treatment, or before initiating a new antineoplastic therapy, whichever comes first.

**Note:** If the last radiographic assessment was performed less than 28 days prior to the last dose of study treatment, it does not need to be repeated.

For the patients who discontinued treatment for reasons other than disease progression or withdrawal of consent, tumour assessments should be continued and documented according to the protocol schedule until disease progression (Section 7.5.1).

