## 3.2. Trial Endpoints

### 3.2.1. Primary endpoint

Radiographic progression-free survival, defined as time from randomisation to radiographic progression as assessed by the investigator according to PCWG3 criteria ([Scher, 2016](#); Appendix 3), or death, whichever occurs first.

*According to the PCWG3 recommendations; radiographic progression is defined as either the appearance of two or more new bone lesions on bone scan or a nodal or visceral progression according to Response Evaluation Criteria in Solid Tumours version 1.1 (RECIST v1.1; [Eisenhauer, 2009](#)). The date of radiographic progression will be the date of the first reported event meeting the above definition (see Appendix 3 & Appendix 4 for further details).*

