## 6. EVALUATION OF TREATMENT EFFICACY AND SAFETY

### 6.1. Efficacy evaluation

Treatment efficacy will be evaluated by measuring changes in tumour size/number of lesions (see Section 7.3.8) and serum PSA levels in response to treatment; according to PCWG3 criteria ([Scher, 2016](#); Appendix 3).

Patient's disease will be assessed at "baseline" (during the screening period) and then every 120 (±14) days after randomisation during the first 2 years and every 180 (±14) days thereafter, until documented radiographic progression, or death, whichever occurs first. For patients who discontinue study treatment for reasons other than radiographic progression, death, or consent withdrawal, investigators will continue to perform disease evaluations during the follow-up period until progression.

The primary evaluation endpoint is radiographic progression-free survival, defined as time from randomisation to radiographic progression according to PCWG3 criteria or death, whichever occurs first.

For secondary evaluation endpoints see Section 3.2.2.

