An EoT visit will be performed within 30 ( $\pm 3$ ) days of study treatment discontinuation for any reason. After the EoT visit, patients will enter the LTFU period and will be followed up for a maximum of 10 years from the date of randomisation. During this time, information will be collected every 180 ( $\pm 14$ ) days regarding survival status, subsequent antineoplastic treatments and the status of ongoing AEs and/or new IP related AEs. Patients who discontinue treatment for reasons other than disease progression (e.g. due to toxicity, patient or investigator decision) will continue to be assessed by clinical/laboratory exam and radiographic imaging according to the protocol schedule, until radiographic progression, or death.

A table summarizing the examination/visit schedule is provided in the "[Schedule of visits and activities](#)" section of the protocol summary.

ADT: Androgen deprivation therapy, bid: Twice a day, CT: Computed tomography, D: Day, EOT: End of treatment, FFPE: Formalin-fixed, paraffin-embedded, MRI: Magnetic resonance imaging, po: Per os (orally), QoL: Quality of life, R: Randomisation, Q: Every, V: Visit, Yrs: Years

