#### 7.4. End-of-treatment visit

Patients will continue to receive study treatment and undergo study procedures as outlined above until radiographic disease progression. Study treatment will be continued for subjects who have increasing PSA values in the absence of radiographic or clinical progression. Although serial PSA measurements will be performed in this study, progression or change in PSA values is not considered a reliable measure of disease progression and should not be used as the lone indicator for discontinuation.

In case of clinical progression without radiographic progression, the investigator should also assess whether it is the patient's best interest to stop study treatment and change to another therapy, or in selected cases, to carry on with the study treatment.

Treatment may also be terminated early at the initiative of either the patient or the investigator for any reason that would be beneficial to the patient, including: unacceptable toxicity, intercurrent conditions that preclude continuation of treatment, or patient request.

If the study treatment is terminated, the ADT should be continued.

Following treatment discontinuation for any reason, the following examinations are to be performed 30 ( $\pm$  3) days after last dose of study treatment, or before initiating a new antineoplastic therapy, whichever comes first:

- Complete clinical examination (major body systems).
- Collection of height and body weight.
- Measurement of vital signs (blood pressure, seated heart rate, body temperature).
- Assessment of ECOG performance status.
- Electrocardiogram (only in case of abnormal results at screening visit, or if clinically indicated by patient symptoms)
- Assessment of ongoing toxicities including pre-existing symptoms and any concomitant therapies received.
- Haematology analysis (see Table 3, page 47).
- Serum chemistry (see Table 3, page 47).
- Measurement of serum PSA and testosterone levels.
- Assessment of patient quality of life using the following tools:
  - EORTC-QLQ-C30 (Appendix 10)
  - EORTC-QLQ-PR25 (Appendix 11)
  - BPI-SF (Appendix 12)

- Assessment of patient geriatric status using the G-CODE assessment tool (Appendix 8).
- **For patients who provide additional informed consent:** Where medically feasible a biopsy should be performed at time of disease progression to collect a treatment-resistant tumour sample.

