#### **7.5.1. Efficacy follow-up**

During the LTFU period, patients who discontinue treatment for reasons other than radiographic disease progression, or withdrawal of consent from the entire study should continue to be assessed by radiographic imaging, PSA and testosterone, ECOG performance status, complete Brief Pain Inventory - Short Form [BPI-SF] and use Opioid therapy according to the protocol schedule, until disease progression or death.

The disease evaluation will be performed according to the methods outlined in Section 7.3.8.

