**Table 5. Censoring rule for primary analysis of radiographic progression-free survival**

Censoring situation	Date of censoring
No baseline assessment	Date of randomisation
No post-baseline assessment and no death prior to first scheduled assessment	Date of randomisation
No radiographic progression or death on study	Date of last tumour assessment
Withdrawn from the study without documented radiographic progression	Date of last tumour assessment

The primary analysis for the rPFS endpoint will be done considering the first radiographic progression observed under study (even if this first radiographic progression is observed under a subsequent line of therapy). As a sensitivity analysis, in case of initiation of a subsequent line of therapy before observing a radiographic progression, the data will be censored at the time of initiation of the salvage treatment.

The final analysis of the primary endpoint will be event-driven, to be performed when at least 197 patients have experienced radiographic progression or death.

Inference for the primary endpoint will be assessed using a two-sided stratified log-rank statistic as the primary analysis. The analysis on stratification factor at randomisation: LATITUDE risk criteria (high risk versus low risk) and ECOG performance status score (0 or 1 vs 2).

A patient is considered as high risk according to the LATITUDE criteria if he has at least two of the three following high-risk factors associated with poor prognosis: a Gleason score of 8 or more (on a scale of 2 to 10, with higher scores indicating more aggressive disease), at least three bone lesions, and the presence of measurable visceral metastasis. He is otherwise considered as low risk ([Fizazi, 2017](#)).

In case the stratification factor does not have sufficient number of patients (less than 3%) and the inferential analyses would be negatively impacted, the stratification factor will not be included as a stratification factor in this analysis.

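### The rule for imaging after treatment stops is worded differently in six places, and two wordings can end scans before the rPFS event

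*Protocol*

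**What the plan says.** Section 3.2.1 gives rPFS as "defined as time from randomisation to radiographic progression as assessed by the investigator according to PCWG3 criteria", or death. Clinical progression is not an event.

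Section 7.4 separates the kinds of progression and allows a stop without a radiographic event: "In case of clinical progression without radiographic progression, the investigator should also assess whether it is the patient's best interest to stop study treatment". The same sentence foresees a switch of therapy.

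The imaging rule after such a stop appears in several places:

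- Section 7.4.1: "For the patients who discontinued treatment for reasons other than disease progression or withdrawal of consent, tumour assessments should be continued and documented", to continue until disease progression, with a reference to 7.5.1.
- Section 7.5.1: admits men who stopped for reasons other than radiographic progression, then runs "according to the protocol schedule, until disease progression or death".
- Section 6.1: "For patients who discontinue study treatment for reasons other than radiographic progression, death, or consent withdrawal, investigators will continue to perform disease evaluations", during follow-up until progression. The preceding sentence of 6.1 sets the general schedule to run until documented radiographic progression or death.
- Section 7: admits men who stopped for reasons other than disease progression, and scans "until radiographic progression, or death".
- Footnote (b) of the schedule of activities: radiographic for entry, unqualified for the end.
- Protocol summary, part C: unqualified for both, and imaging also ends when a new antineoplastic treatment starts.

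Section 10.3.2 states the primary analysis as "considering the first radiographic progression observed under study (even if this first radiographic progression is observed under a subsequent line of therapy"). Table 5 censors men without radiographic progression or death at the last tumour assessment.

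**The concern.** The analysis needs every man's first radiographic progression, including one that occurs on a later therapy. That requires one imaging rule for all sites, tied to the same event as the endpoint.

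The protocol uses the qualified term when it means it, for example in the treatment-discontinuation reasons of section 5.6, and it makes clinical progression-free survival a key secondary endpoint. An unqualified term can therefore be read to include clinical worsening. A man who stops for clinical progression is probably closer than average to radiographic progression. If his scans end there, his censoring depends on prognosis, which the log-rank test and Cox model do not allow for. Section 7.5 says no study-specific evaluations take place in long-term follow-up beyond those in 7.5.1, so only routine-care imaging would remain. A statistical analysis plan cannot recover scans that were never done.

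**Working it through.** **1. The wordings side by side**

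| Place | Who continues imaging | When imaging ends |
|---|---|---|
| Summary, part C | stopped for other than disease progression | disease progression, new antineoplastic treatment, or death |
| Schedule, footnote (b) | other than *radiographic* progression | disease progression |
| 6.1, post-treatment sentence | other than *radiographic* progression, death, consent withdrawal | progression |
| 7 | other than disease progression | *radiographic* progression or death |
| 7.4.1 | other than disease progression or consent withdrawal | disease progression |
| 7.5.1 | other than *radiographic* progression or consent withdrawal | disease progression or death |

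No row is qualified in both columns. Section 7.4.1 and the summary are qualified in neither.

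**2. Three men traced through the rules**

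- *Stops for clinical progression and changes therapy.* 7.4.1 and the summary, read literally, ask for no further scheduled scans. 7.5.1, footnote (b) and 6.1 admit him to further imaging. Section 10.3.2 needs his scans.
- *Stops for toxicity, later progresses clinically only.* Under 7.4.1, 7.5.1, footnote (b) and the summary he has arguably reached the end of imaging. Under section 7 and the general sentence of 6.1 he has not.
- *Stops for toxicity and starts a new therapy without progression.* Only the summary ends his imaging, but it does so without ambiguity and against section 10.3.2.

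**3. The plan's own figures reproduce**

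Inputs from section 10.1: HR 0.65, two-sided alpha 0.05, power 85%, medians 12 and 18.5 months, drop-out hazard 0.014 (taken as per month), 150 per arm, the accrual table, and 197 events at month 75.

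- Schoenfeld: 4 × (1.960 + 1.036)² / (ln 0.65)² = 4 × 8.978 / 0.1856 = 193.5, so 194.
- Freedman: (1.65 / 0.35)² × 8.978 = 199.5, so 200. The stated 197 lies between.
- Lan-DeMets O'Brien-Fleming boundaries at 138/197: Z = 2.437 and 2.000, as stated. Group-sequential power at 197 events is 85.1%.
- Expected events: λ/(λ+η) × [1 − exp(−(λ+η)f)], averaged over the accrual table, with f the follow-up time, λ = ln 2/12 = 0.0578 and 0.65 × 0.0578 = 0.0375, and η = 0.014. At month 75 this gives 196.7 events and 19.8% drop-out (stated: 197 and 19.3%).

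So no stated figure is wrong on this point.

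**4. What early exit could cost (illustration only)**

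The documents give no rate of stopping for clinical progression. Assume an extra hazard of leaving imaging, equal in both arms and unrelated to prognosis, added to 0.014:

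| Extra hazard per month | Events at month 75 | Schoenfeld power at that count | Month of 197th event |
|---|---|---|---|
| 0 | 197 | 85.6% | 75 |
| 0.005 | 186 | 83.5% | 84 |
| 0.01 | 176 | 81.5% | 132 |
| 0.02 | 158 | 77.4% | not reached (limit 173) |

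These are upper bounds on event loss, because deaths stay observable in follow-up.

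Now let exit depend on prognosis: men leave imaging 0 to 6 months before radiographic progression, with later deaths ignored.

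| Share leaving, control / darolutamide | Hazard ratio |
|---|---|
| none | 0.650 |
| 10% / 10% | 0.645 |
| 30% / 30% | 0.637 |
| 20% / 10% | 0.716 |
| 10% / 20% | 0.580 |

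Counting later deaths as events, and assuming a lead of 1 to 6 months, softens the shift. At 20%/10% the ratio is about 0.68 to 0.69 with 10 to 13 events missing at month 75. With the shares reversed it is about 0.61.

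**The case against.** The strongest reply is that the protocol, read as a whole, means radiographic. Section 7.5.1 is the operative rule for follow-up: 7.4.1 refers to it, and its entry condition expressly keeps a man who stopped for clinical progression. If its end condition included clinical progression, he would meet the end on entry and the clause would have no effect. Section 5.6 lists radiographic progression as its only progression reason, so a clinical stop falls under the investigator's decision, which section 7 names among the reasons after which assessment continues.

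Most of this stands. A reader might infer that 7.4.1 and 7.5.1 both release these men; the documents do not support that, because the entry conditions of 7.5.1 and footnote (b) say the opposite. The reply does not remove the defect. The entry condition of 7.4.1 still conflicts with that of 7.5.1. The unqualified end still leaves the second man in the trace uncertain. The new-therapy stop in the summary is a plain contradiction of section 10.3.2.

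A reader might also infer a definite bias towards 1 or a definite loss of power. That is not supported either. The shares, lead times and direction are assumptions, the simulations suppose that every such man goes unscanned, and power at calendar month 75 is not the trial's power, because the final analysis waits for 197 events.

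**Conclusion.** The point holds as an inconsistency that bears on ascertainment of the primary endpoint. It is not a demonstrated bias. Six statements of one rule disagree, and a site that follows 7.4.1 or the summary as written could end imaging before the rPFS event, against section 6.1 and section 10.3.2.

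The size cannot be computed from the documents. Under the assumptions shown, equal loss in both arms barely moves the hazard ratio and mainly delays the 197-event analysis. Differential loss is the real risk and can push the estimate either way, roughly 0.58 to 0.72 around a true 0.65 when the shares are 20% and 10%. The sample size and event target need no change.

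**What to change.** Reconcile the protocol summary (part C), schedule footnote (b), and sections 6.1, 7, 7.4.1 and 7.5.1 to one sentence: imaging continues on schedule after any stop of study treatment, including a stop for clinical progression and after a change of therapy, until radiographic progression as defined in section 3.2.1, death or withdrawal of consent. Both the entry and the end condition need the qualifier, and the new-therapy stop in the summary has to go. Correcting 7.4.1 alone would leave the other conflicts in place.

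Section 7.5.1 and footnote (b) also govern ECOG status, BPI-SF and other follow-up items, so the imaging rule is best stated separately if the sponsor does not want the same end point for those.

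The cost is wording in six places and a note to sites. No visit type is added, since 6.1 already requires post-treatment evaluations. The small downside is more scans in men who have changed therapy. The current amendment reports about 115 of 300 men enrolled, so about 185 are still to come, and an early correction protects most of the follow-up.

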### 7.5. Follow-up

Long-term follow-up assessments will be performed for all patients every 180 ( $\pm$  14) days following the EoT visit.

The following information will be collected at each LTFU assessment:

- Patients survival status.
- Subsequent antineoplastic therapies (including regimen administered [drug, dose, frequency, mode], start and stop dates).
- Efficacy data (including response to subsequent antineoplastic therapies, dates of progression and evaluation of serum PSA levels).
- Status of ongoing AEs and/or new treatment-related AEs.

No study specific evaluations will be performed during the LTFU period, other than those described in Section 7.5.1 below. Data collection will be limited to that information which is available in the patient's medical file and evaluations performed as part of patients continued treatment at the site, or obtained via communication with the patients treating physician or via telephone contact with the patient.

Long-term follow-up will continue until death, withdrawal of consent, or 10 years after date of patient randomisation, whichever occurs first.

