#### Other secondary endpoints

- Time to worsening in prostate cancer-related urinary symptoms, defined as an increase from baseline of greater or equal to 8 points in the urinary symptom scale/score (PRURI) measured using the prostate cancer module of the European organisation for research and treatment of cancer (EORTC) quality of life questionnaire (QLQ) (EORTC-QLQ-PR25).
- Time to next symptomatic skeletal event, defined as the time from randomisation until first occurrence of one of the following: a symptomatic fracture, radiation or surgery to bone or a spinal cord compression (PCWG3 criteria).

**Note:** *The occurrence of these events will be determined by investigator evaluation. No systematic X-Ray will be performed.*

- Complete PSA response (defined as PSA  $\leq$  0.2 ng/ml) at 6 months.
- Prostate cancer-specific survival, defined as the time from randomisation to the date of death due to prostate cancer (deaths due to other causes will be censored).
- Time to deterioration for EORTC QLQ-PR25 symptom subscales, defined as the first decline in the HRQoL score from baseline equal to or greater than the minimally important difference (MID; a measure of clinical significance) defined as half the standard deviation of the baseline value for each subscale.
- Time to first subsequent systemic anti-cancer therapy (SACT) defined as the time from randomisation to the date of initiation of any SACT for CRPC, following initiation of the study treatment.
- Efficacy of subsequent SACT will be assessed according to rPFS, OS, and PFS after next line of treatment (PFS2); defined as the time from randomisation to second objective disease progression, or death from any cause, whichever first.
- Health related quality of life will be evaluated using the EORTC-QLQ-C30, EORTC-QLQ-PR25 and BPI-SF questionnaires.
- Geriatric status will be evaluated using the Geriatric Core Dataset (G-Code) assessment.
- Impact of sarcopenia on overall survival will be evaluated by comparing the distribution of overall survival between sarcopenic and non-sarcopenic patients.
- Impact of sarcopenia on treatment response will be evaluated by comparing rate of response in sarcopenic and non-sarcopenic patients.

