### **8.1.3. Adverse Event Reporting**

All AEs that occur from the time the informed consent form is signed until 30 days after the last dose of IMP must be recorded by the investigator in the patients' medical file and reported in the eCRF (see Section [Erreur ! Source du renvoi introuvable.](#) for the reporting requirements of AEs which meet any serious criteria). The investigator will make every attempt to follow all AEs until resolution and to report their outcome in the eCRF.

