The proportional hazard assumption will be assessed graphically by plotting log (-log[estimated survival distribution function]) against log(survival time). The resulting graphs should have approximately parallel lines when the assumption holds. If the proportional hazards assumption is reasonably met, then a stratified Cox proportional hazard model will be used to estimate the treatment effect using Hazards Ratio (HR) and its two-sided 95% confidence interval (95%CI). If the proportional hazards assumption is violated, then the inference remains statistically valid for testing equality in survival distributions. In addition, rPFS will be descriptively summarized using Kaplan-Meier methodology, including medians and two-sided Rothman's 95%CI ([Kaplan, 1958](#); [Rothman, 1978](#)).

Stratification factors will include:

- LATITUDE risk criteria (high risk versus low risk, [Fizazi, 2017](#))
- ECOG performance status score (0 or 1 vs. 2).

If final analysis of the primary endpoint meets the pre-specified hypothesis (see Section 10.1), an additional sensitivity analysis of rPFS will be performed using the results of a centralised disease evaluation by an independent review committee (IRC).

All the other secondary time to event endpoints (namely, CRPC-free survival, clinical progression-free survival, time to worsening in prostate cancer-related urinary symptoms, time to next symptomatic skeletal event, prostate cancer specific survival and overall survival, time to first subsequent SACT and time to second subsequent SACT) will be analysed using the same methods as the primary endpoint (stratified two-sided log-rank test, stratified Cox proportional hazards models). Secondary endpoints will be analysed according to the investigators' assessment of response. Censoring rules for these endpoints will be detailed in the SAP.

The median follow-up will be estimated using the inverse Kaplan-Meier method ([Schemper, 1996](#)).

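### No follow-up item names symptomatic skeletal events after the end-of-treatment visit, although the endpoint runs from randomisation in all randomised patients

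*Protocol*

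**What the plan says.** **The endpoint.** Protocol Section 3.2.2 lists it among the other secondary endpoints: "Time to next symptomatic skeletal event, defined as the time from randomisation until first occurrence of one of the following", namely symptomatic fracture, radiation or surgery to bone, or cord compression. On how it is established, the note reads "The occurrence of these events will be determined by investigator evaluation. No systematic X-Ray will be performed". No time limit is attached.

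**The analysis.** Section 10.2 puts all secondary efficacy endpoints on the ITT population. Section 10.3.2 includes "time to next symptomatic skeletal event, prostate cancer specific survival and overall survival" in the list of endpoints that "will be analysed using the same methods as the primary endpoint (stratified two-sided log-rank test, stratified Cox proportional hazards models". It leaves their censoring rules to the SAP, which was not available. Section 10.3.7 treats every endpoint outside the three key secondaries as exploratory, without multiplicity adjustment.

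**Collection after EoT.** Section 7.5 lists survival, subsequent antineoplastic therapy, "Efficacy data (including response to subsequent antineoplastic therapies, dates of progression and evaluation of serum PSA levels", and ongoing or treatment-related adverse events. It adds that "No study specific evaluations will be performed during the LTFU period, other than those described in Section 7.5.1 below". Section 7.5.1 covers patients who stopped for reasons other than radiographic progression. They "should continue to be assessed by radiographic imaging, PSA and testosterone, ECOG performance status, complete Brief Pain Inventory", with opioid use, until progression or death. The follow-up column of the schedule has no SSE row, and its concomitant-therapy entry ends at progression. Under Section 8.1.3, adverse events "until 30 days after the last dose of IMP must be recorded by the investigator". Under Section 8.2.2, later serious events are reportable only if related to the treatment or the research.

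**The concern.** While a patient is on treatment, every visit records all adverse events, symptoms and concomitant therapies, so a fracture or cord compression has somewhere to go. After EoT, a new disease-related skeletal event matches no named item, yet the endpoint clock is still running.

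Section 7.5.1 sharpens the contrast. ECOG status, pain score and opioid use, which feed clinical progression-free survival, are carried into follow-up by name, and SSE is not.

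The date at which dependable capture ends is not neutral. Study treatment normally stops at radiographic progression, which the trial expects darolutamide to delay. If skeletal risk rises after progression, the least well observed period is the one with the highest risk, and it starts sooner in the control arm. A SAP can choose a censoring date, but it cannot supply events that were not recorded.

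**Working it through.** **1. Reproduce the plan's own figure.** Inputs from Section 10.1: HR 0.65 (medians 12 and 18.5 months), two-sided 5%, 85% power, 1:1, 197 events at month 75.

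- Schoenfeld: 4(1.960 + 1.036)² / (ln 0.65)² = 4 × 8.98 / 0.1856 ≈ 194.
- Freedman: 8.98 × (1.65)² / (0.35)² ≈ 200.
- Simulation with the Section 10.1 accrual table, exponential rPFS and a drop-out hazard of 0.014 (taken as monthly): 196.5 events at month 75, with 19.8% drop-out (plan: 19.3%).

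The 197 events and the 75 months are sound, so the same accrual and rPFS model can carry the SSE check.

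**2. Model for SSE.** The protocol gives no SSE rate. All of the following are assumptions:

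- hazard λ = 0.005 or 0.01 per month before the rPFS event, and kλ after it, with k = 1, 2 or 3;
- 25% of rPFS events are deaths;
- median survival after progression of 12 or 24 months;
- no drop-out, and no direct treatment effect on SSE other than through delayed progression.

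Full collection observes SSE until death or cut-off. Truncated collection also stops one month after the rPFS event. Share lost = 1 − (events kept / events with full collection). Cut-offs are month 75 (primary analysis) and month 180 (60 months of accrual plus the 10 years to the final analysis in Section 10.1). The month-180 runs do not apply the 10-year cap per patient.

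**3. Results at month 75, λ = 0.01, 24 months' survival after progression.**

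| k | Events, full | Events, truncated | Lost | Lost, control / experimental | HR, full | HR, truncated |
|---|---|---|---|---|---|---|
| 1 | 68 | 46 | 32% | 38% / 27% | 1.01 | 1.02 |
| 2 | 86 | 47 | 45% | 51% / 39% | 0.91 | 1.00 |
| 3 | 100 | 49 | 51% | 57% / 46% | 0.88 | 1.00 |

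Mean observable time falls from 25.5 to 15.2 months in control and from 28.1 to 19.7 in experimental.

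**4. Range over all 12 scenarios per cut-off.**

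| Cut-off | Smallest loss | Largest loss | Scenarios above 50% |
|---|---|---|---|
| Month 75 | 25% (61 to 46 events) | 55% (58 to 26) | 2 of 12 |
| Month 180 | 31% (81 to 56) | 67% (98 to 33) | 5 of 12 |

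The control arm loses more in every scenario, by about 9 to 12 percentage points. The pull towards 1 appears only when the hazard rises after progression. With k = 1 events are lost, but the HR at month 75 barely moves.

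**5. Why a censoring rule alone does not help.** Censoring at EoT gives the truncated column above. Censoring at last contact would instead count missed events as event-free time. In the k = 2 row the retained fractions are 0.49 (control) and 0.61 (experimental), so the experimental-to-control ratio of event counts is multiplied by 0.61 / 0.49 ≈ 1.24.

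**6. Precision even with full collection.** With d events, the standard error of log HR is about 2/√d. For the k = 2 row, 2/√86 = 0.216, the 95% interval around 0.908 is about 0.59 to 1.39, and two-sided power is about 7%.

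**The case against.** The strongest reply is that the protocol does not exclude SSE from follow-up. The efficacy item in Section 7.5 is open-ended, SSE is an efficacy endpoint, and its occurrence rests on investigator evaluation, for which the medical file, the treating physician or a telephone call would do. The schedule has no SSE row at any visit, so a blank in the follow-up column does not mark a stop. There are also partial routes: therapy records may show bone radiotherapy, and Section 8.2.1 sends serious progression-related events and surgery for the disease to the eCRF, with no end date of its own. All of this stands. A reader might infer that SSE has no collection point at all after EoT, and the text does not support that. What remains is that none of these routes asks for SSE by name. The therapy fields are written for drug regimens, and the Section 8.1.3 window may govern the eCRF reporting in Section 8.2.1. Uneven capture across 100 sites is the likely result.

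Two other strong readings also fail:

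- **Most events are lost.** The protocol gives no rate. At month 75 the loss exceeds half in only 2 of 12 scenarios. A run with OS medians of 42/50 months and a threefold to fivefold rise in hazard at progression lost about two-thirds or more (67 events to 22; 89 to 24). But Section 1.2 gives 36.5 months for the control arm of the reference trial, and Section 10.1 expects additional deaths from other causes here.
- **SSE follow-up ends at progression, earlier in control.** No section says so. Censoring is left to the SAP, men who stop for other reasons lose general adverse-event recording 30 days after the last dose rather than at progression, and the earlier date in control is the design alternative, not an observed fact.

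Finally, the endpoint is exploratory and unpowered. A null SSE result would be weak evidence even with full collection.

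**Conclusion.** The point holds as a gap between an endpoint and its data collection. SSE is counted from randomisation and compared by ITT, but after EoT no item names it and adverse-event collection narrows to ongoing or treatment-related events. Followed as written, the plan gives dependable SSE data up to a date linked to progression and patchy data beyond it.

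The possible loss is roughly 25% to 67% of first events, depending on the assumed hazards, survival after progression and cut-off. If the design alternative holds, the loss is larger in control. If, in addition, skeletal risk doubles or triples after progression and darolutamide acts on SSE only by delaying progression, an HR of about 0.88-0.91 at month 75 becomes about 1.0. That shift is well inside sampling error for this endpoint. The primary analysis, the sample size and the key secondary analyses are unaffected. The change is worth making because it is cheap and removes a potentially differential loss, not because a confirmatory conclusion depends on it.

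**What to change.** - Add symptomatic skeletal events (type and date) as a named item in Sections 7.5 and 7.5.1 and as an entry in the follow-up column of the schedule. It should apply to all patients every 180 days until death or the end of follow-up, whatever the reason for stopping treatment.
- Take the information from the sources Section 7.5 already allows: medical file, treating physician or telephone contact.
- Back-fill patients already in long-term follow-up. About 115 of 300 were enrolled at this amendment, so most of the follow-up is still to come.
- In the SAP, censor event-free patients at the last contact at which SSE status was ascertained, not at last contact for survival.

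The cost is one extra eCRF item at contacts that already take place, plus some retrospective data entry. No visit or examination is added.
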